Amendment 3.2	30APR2020	The Netherlands, Japan, Denmark and Czech Republic specific amendment
Amendment 2.4	30APR2020	Japan specific amendment
Amendment 3.3	08JUL2020	The Netherlands, Japan, Denmark and Czech Republic specific amendment
Amendment 4.1	19JAN2021	The Netherlands, Germany, Japan, Denmark and Czech Republic specific amendment
Amendment 4.2	25JUN2021	Germany specific amendment

This statistical analysis plan (SAP) only considers the latest version of the protocol, and of the protocol amendments, as listed above.

	
Statistical Analysis Plan
	

ARGX-113-1705
	
Final Analysis
	
Final 1.0 of 20SEP2022

LIST OF ABBREVIATIONS

1704	ARGX-113-1704
1705	ARGX-113-1705
Ab	Antibody
AChR	Acetylcholine receptor
ADA	anti-drug antibody
ADaM	analysis data model
ADYP	relative day in period
AE	adverse event
AESI	adverse event of special interest
ALQ	above limit of quantification
BLQ	below limit of quantification
bpm	beats per minute
CI	confidence interval
CKD-EPI	Chronic Kidney Disease Epidemiology Collaboration
CnB	cycle n baseline
CRF	case report form
DBP	diastolic blood pressure
DSMB	data safety monitoring board
ECG	electrocardiogram
eGFR	estimated glomerular filtration rate
EoA	end of part A of the study
EU	European Union
gMG	generalized myasthenia gravis
HR	heart rate
ICF	informed consent form
ICH	International Council for Harmonisation
IMP	investigational medicinal product
ITP	inter treatment period
ITT	Intent-To-Treat
J-NDA	Japan new drug application
LLOQ	lower limit of quantification
mITT	Modified Intent-To-Treat

	Statistical Analysis Plan	
ARGX-113-1705	Final Analysis	Final 1.0 of 20SEP2022

MAA	marketing authorisation application
MedDRA	Medical Dictionary for Regulatory Activities
MG-ADL	myasthenia gravis - activities of daily living
MuSK	muscle-specific kinase
NAP	not applicable
OLE	open-label extension
PD	pharmacodynamics
PYFU	patient years of follow-up
QTc	corrected QT interval
QTcB	Bazett's corrected QT interval
QTcF	Fridericia's corrected QT interval
RO	roll-over
SAP	statistical analysis plan
SAF	safety analysis set
SBP	systolic blood pressure
SD	standard deviation
SE	standard error
SGS CR	SGS Clinical Research
SoA	schedule of assessments
SOP	standard operating procedure
STAT	statistics
TEAE	treatment-emergent adverse event
ULOQ	upper limit of quantification
VS	vital signs
WHO	World Health Organisation
WI	work instruction

1. INTRODUCTION

This SAP describes the final statistical analysis to be performed for the ARGX-113-1705 (BE-80-1801535) study.

This SAP covers the safety, efficacy, PD, immunogenicity and general characteristics parts of the statistical analysis. It specifies the analysis displays to be presented and describes the methods and procedures in a more elaborated way than in the statistical methods section of the protocol.

The statistical analysis will process and present the results following the International Council for Harmonisation (ICH) standards, in particular the ICH-E3, ICH-E6, and ICH-E9 guidelines.

1.1 STUDY OBJECTIVES

According to the protocol, the primary objective of this study is:

- To evaluate the long-term safety and tolerability of ARGX-113 in acetylcholine receptor antibody (AChR-Ab) seropositive patients.

According to the protocol, the secondary objective of this study is:

- To evaluate the long-term safety and tolerability of ARGX-113 in the overall population (AChR-Ab seropositive and AChR-Ab seronegative patients).

According to the protocol, the tertiary objectives of part A of this study are:

- To evaluate the disease severity as assessed by total Myasthenia Gravis Activities of Daily Living (MG-ADL) score changes in AChR-Ab seropositive patients.
- To evaluate the disease severity as assessed by total MG-ADL score changes in the overall population (AChR-Ab seropositive patients and AChR-Ab seronegative patients).
- To evaluate disease severity as assessed by total Quantitative Myasthenia Gravis (QMG) score changes in AChR-Ab seropositive patients.
- To evaluate disease severity as assessed by total QMG score changes in the overall population (AChR-Ab seropositive patients and AChR-Ab seronegative patients).
- To evaluate the effect of ARGX-113 on pharmacodynamics (PD) (total immunoglobulin G [IgG], IgG subtypes, autoantibodies [anti-AChR antibodies and anti-muscle-specific kinase (MuSK) antibodies]).

According to the protocol, the tertiary objectives of part A and B of this study is:

- To evaluate the immunogenicity of ARGX-113.

1.2 STUDY DESIGN

This is a phase 3 multicentre, single arm, Open-Label Extension (OLE), Follow-on study of ARGX-113-1704 assessing the long-term safety and tolerability of (intravenous) ARGX-113 in adults with generalized myasthenia gravis (gMG).

	Statistical Analysis Plan	
ARGX-113-1705	Final Analysis	Final 1.0 of 20SEP2022

At the End of Study visit of trial ARGX-113-1704, eligible patients were offered the option to roll over into this trial. Hence, the maximum number of patients in this trial is the number of patients who participated in trial ARGX-113-1704.

Within trial ARGX-113-1705, a variable number of Treatment periods (i.e. 4 weekly infusions of ARGX-113 infused over a period of 3 weeks) were administered to eligible patients on an “as needed basis” on top of their SoC in Treatment Periods.

The anticipated study duration was a maximum of 3 year after entry into the OLE. After the first year (part A), the number and frequency of assessments decreased for the remaining time in the study (part B). During part B, patients had the opportunity to enter study ARGX-113-2002 to be treated with subcutaneous ARGX-113 and PH20.

The schedule of assessments is in appendix [9.2](#).

1.3 EXPECTED SAMPLE SIZE

The maximum number of patients in ARGX-113-1705 is the number of patients who participated in trial ARGX-113-1704 which is 167.

1.4 RANDOMISATION AND BLINDING

Not applicable.

1.5 INTERIM ANALYSIS

Interim analyses were performed. These are described in separate SAPs.

1.6 SOFTWARE

SAS version 9.4 or later will be used for programming.

1.7 VALIDATION MODEL

SGS statistics (STAT) standard operating procedures (SOPs) and work instructions (WIs) as effective at the project start will be followed throughout the project, provided the applicable regulatory requirements are still met.

Analysis Data Model (ADaM) datasets, analysis tables and listings will be validated according to model B: review by an independent person.

	Statistical Analysis Plan	
ARGX-113-1705	Final Analysis	Final 1.0 of 20SEP2022

2. GENERAL METHODOLOGY

2.1 ANALYSIS SETS

2.1.1 *Analysis sets*

The following analysis sets will be considered in the statistical analysis:

Roll-over set (RO):	patients who rolled over from the 1704 study
Safety analysis set (SAF):	all patients who received at least one dose or part of a dose.

All analyses will be performed on the safety analysis set.

A patient is considered to have rolled over if he has signed the ARGX-113-1705 specific informed consent, defined as having a complete informed consent signature date in the database.

The AChR-Ab seropositive subset population is defined based on the stratification factor as randomized in the 1704 study.

2.1.2 *As planned versus as actual analysis*

The actual treatment of the patient will be considered for both 1704 and 1705 studies (see section 2.4.2).

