7.2.1. Adverse Events

The investigator is responsible for recording all AEs observed during the trial from the time the patient signs the ICF until the last contact of the patient.

Definition of AE: An AE is any untoward medical occurrence in a clinical trial patient whether or not a pharmaceutical product is administered, and which does not necessarily have a causal relationship with this treatment. An AE can therefore be any unfavorable and unintended sign (including an abnormal laboratory finding), symptom, or disease temporally associated with the use of a medicinal product or efgartigimod, whether or not considered related to the medicinal product or efgartigimod.

An AE can also be a new disease or exacerbation of an existing disease (a worsening in the character, frequency, or severity of a known condition), if considered clinically relevant by the investigator.

Abnormal laboratory values, or test results, physical examination findings, and other abnormal investigational findings (ie, ECG) should not be reported as AEs unless they are considered clinically significant, eg, require therapy (eg, hematologic abnormality that requires transfusion or hematological stem cell support) or lead to treatment discontinuation.

Death is not considered an AE but an outcome.

MG disease worsening, if considered clinically relevant by the investigator, can be reported as AE, provided that it is supported by a clinically relevant change in total MG-ADL score (as compared to SEB). The investigator should contact the sponsor in case of clinically relevant worsening of the disease.

Adverse Drug Reaction (ADR): Any untoward and unintended response in a patient to efgartigimod, which is related to any dose administered to that patient.

Definition of Serious AE (SAE): An SAE, experience or reaction, is any untoward medical occurrence (whether considered to be related to efgartigimod or not) that at any dose:

- Results in death
- Is life-threatening (the patient is at a risk of death at the time of the event; it does not refer to an event, which hypothetically might have caused death if it was more severe)
- Requires inpatient hospitalization or prolongation of existing hospitalization. However, a planned hospitalization related to the administration of efgartigimod is not considered an SAE

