8.2. Analysis Populations

The analysis population will consist of all patients who rolled over from trial ARGX-113-1704.

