8.3. Patient Disposition, Characteristics and Concomitant Medication

A tabular presentation of the patient disposition will be provided. It will include the number of patients enrolled, completed (by cycle), as well as the number of early discontinuations (including rescued patients), with reasons for discontinuation from trial treatment or trial and major protocol deviations.

A listing will be presented to describe dates of SEB, completion or early discontinuation and the reason for early discontinuation, if applicable, for each patient.

Patient characteristics will be recorded prior to enrollment and will be listed and summarized. Overall summaries will include descriptive statistics for continuous measures (number of observations, mean, standard deviation, median, minimum and maximum) and for categorical measures (sample size, frequency, and percent). Patient characteristics include but are not limited to age, sex, race, weight, and body mass index (BMI).

Use of concomitant medication will be summarized with frequency and percentage. All concomitant medications used will be listed.

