8.4. Statistical Methods

8.4.1. Primary and Secondary Endpoint Analyses

All endpoints will be summarized in all enrolled patients and by means of descriptive statistics. Frequency tables will be made for all binary variables, ie, AEs, by cycle and overall.

Summary statistics will be provided for the continuous endpoints (eg, laboratory values, vital signs, ECGs) in terms of absolute values and changes from TP₁B by cycle and available time points.

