6. CHANGES TO THE PLANNED ANALYSIS

6.1 CHANGES NOT COVERED BY PROTOCOL AMENDMENTS BEFORE DATABASE LOCK

NAP

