16.2.7.1 Adverse Events SAF

16.2.7.2 Serious Adverse Events SAF

16.2.7.3 Fatal Adverse Events RO

16.2.7.4 Treatment Emergent Adverse Events Leading to Discontinuation of Study Drug SAF

	Statistical Analysis Plan	
ARGX-113-1705	Final Analysis	Final 1.0 of 20SEP2022

16.2.7.5	Treatment Emergent Adverse Events Leading to Interruption of Study Drug	SAF
16.2.7.6	Treatment Emergent Adverse Events of Special Interest	SAF
16.2.7.7	Infusion-Related Reactions	SAF
16.2.7.8	COVID-Related Events	SAF
LABORATORY DATA		
16.2.8.1	Laboratory Test Results for Subjects with Abnormal Values	SAF
VITAL SIGNS		
16.2.9.1	Vital Signs Results for Subjects with Abnormal Values	SAF
ECG		
16.2.10.1	ECG Results for Subjects with Abnormal Values	SAF
SUICIDALITY ASSESMENT		
16.2.11.1	Suicidality assessment for Subjects with Abnormal Values	SAF
IMMUNOGENECITY		
16.2.12.1	Anti-drug Antibodies and Neutralizing Antibodies	SAF

Statistical Analysis Plan

ARGX-113-1705

Final Analysis

Final 1.0 of 20SEP2022

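### The SAP limits the discontinuation tables and the discontinuation, AE and SAE listings to patients dosed in 1705, although the protocol covers everyone who rolled over and the SAP text promises complete listings

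*SAP*

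**What the plan says.** **Protocol.** Section 8.2 sets a population with no dosing condition: "The analysis population will consist of all patients who rolled over from trial ARGX-113-1704". Section 8.4.1 applies the same idea to the primary and secondary safety endpoints: "All endpoints will be summarized in all enrolled patients". Section 8.3 describes the disposition table: "It will include the number of patients enrolled, completed (by cycle), as well as the number of early discontinuations (including rescued patients", with reasons. It also asks for a patient-by-patient listing of completion or early discontinuation and the reason. Section 7.2.1 makes the investigator responsible for "recording all AEs observed during the trial from the time the patient signs the ICF until the last contact of the patient". The introduction to section 8 says that changes to the analysis methods will be mentioned in the SAP.

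**SAP.** Section 2.1.1 defines a roll-over set (RO), which needs only a complete 1705 consent date, and a safety analysis set (SAF), which needs at least part of one dose. It then states "All analyses will be performed on the safety analysis set". The index in section 8 labels the outputs to match, for example "16.2.7.2 Serious Adverse Events SAF". Section 3.1 nevertheless promises to list everything the CRF collects on study and treatment discontinuation. Section 5.1.3 promises to list every AE, including those before treatment. Section 6.1, headed "CHANGES NOT COVERED BY PROTOCOL AMENDMENTS BEFORE DATABASE LOCK", is marked not applicable, as are 6.2 and 6.3.

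**The concern.** The two sets differ by the patients who sign the 1705 consent and never receive a dose. The design allows for them, because entry can be into an inter-treatment period (ITP0) and dosing is as needed.

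This group can be mixed. Some patients may do well enough never to qualify for treatment. Others may withdraw, have an SAE, or be rescued before a first 1705 dose. Long-term safety is the primary objective, and a disposition account that starts from dosed patients does not account for everyone enrolled. Serious events collected under the protocol would have no place in the final outputs unless they were fatal.

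**Working it through.** No sample size or error rate is involved, so the check compares the texts and the set label on each output.

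**1. Can a rolled-over patient remain undosed?** Yes.
- SAP 2.1.1 counts a patient as rolled over on consent alone.
- SAP 2.2.1 and Protocol 5.1 allow entry at ITP0.
- Protocol 6.1 restricts dosing to patients who need it and qualify.
- Protocol 4.1 (Part A) requires MG-ADL criteria. It withholds treatment from patients with infection or other significant disease, who stay in the trial on alternative MG treatment.
- Protocol 4.4 discontinues rescued patients from the trial in Part A.

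**2. Which set does each relevant output use?**

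| Output | Protocol | SAP text | SAP section 8 |
|---|---|---|---|
| Discontinuation tables 14.1.1.9, 14.1.1.10 | enrolled patients (8.3) | SAF (2.1.1) | SAF |
| Discontinuation listing 16.2.1.1 | each patient (8.3) | all CRF information (3.1) | SAF |
| AE listing 16.2.7.1 | AEs collected from consent (7.2.1) | all AEs, pre-treatment included (5.1.3) | SAF |
| SAE listing 16.2.7.2 | AEs collected from consent (7.2.1) | all AEs (5.1.3) | SAF |
| Fatal AE listing 16.2.7.3 | AEs collected from consent (7.2.1) | SAF (2.1.1) | RO |
| Analysis sets, Table 14.1.1.1 | – | number in each set (3.1) | RO |

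**3. Count over the whole index.**
- Tables: 73 = 72 on SAF + 1 on RO (14.1.1.1).
- Listings: 27 = 25 on SAF + 1 on RO (16.2.7.3) + 1 with no set shown (16.2.6.5, anti-MuSK).

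**4. What is left for a patient in RO but not in SAF?** The patient is counted in Table 14.1.1.1, and a fatal AE would be listed in 16.2.7.3. No indexed output labelled RO carries a discontinuation reason or a non-fatal AE or SAE. SAP 5.1.3 sends ITP0 events to listings only, so as indexed they appear only for patients who are dosed later.

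**5. Do the derivations cover such a patient?** Not fully. SAP 2.2.1 ends ITP0 one minute before the first administration in cycle 1. A patient with no administration has no defined period end.

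**6. How many patients?** The number is RO minus SAF, and neither count is given. SAP 1.3 gives only a ceiling of 167, the number who took part in 1704.

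**The case against.** **SAF is right for much of the analysis.** Protocol 7.2 ties the safety evaluation to patients with at least one dose, and Protocol 7.2.1 starts TEAEs at the first administration. Changes from TP1B or TPnB and cycle summaries have no meaning without a dose. A reader might infer that the AE tables are also on the wrong set. The documents do not support that, because these are TEAE tables and SAF suits them. This part of the objection stands in full.

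**The events are not lost altogether.** The SAP text promises complete listings, so the index labels may be a slip. Deaths are listed on RO. Protocol 7.2.1.2 requires SAEs to be reported within 24 hours, and the DSMB reviews safety data. All this stands, so the gap concerns the indexed outputs of this SAP, not the trial's safety reporting as a whole. But a programmer works from 2.1.1 and the index, and both say SAF.

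**Protocol 11.2 asks for a completed eCRF for each patient who receives efgartigimod.** It does not exempt the others. Protocol 7.2.1.2 requires AEs to be recorded in the eCRF from consent.

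**The choice of set is open.** SAP 2.1.1 defines both sets and says which is used, and the protocol does not require an entry in 6.1 specifically. A reader might infer concealment, which the text does not bear out. It is a departure stated in one section and not identified as a change in the section meant for that.

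**The group may be narrow.** A Part A patient who meets the criteria is to start treatment unless infection or other significant disease prevents it. This is fair, and it limits the likely size.

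**Conclusion.** The point holds for the discontinuation tables and for the discontinuation, AE and SAE listings. Followed as written, the plan departs from Protocol 8.2 and 8.3, contradicts SAP 3.1 and 5.1.3, and does not record the departure in SAP 6.1. The consequence is that no discontinuation reason and no non-fatal AE or SAE is shown for a patient who rolled over but was never dosed in 1705.

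The size is unknown and may be zero. A reader might apply an assumed never-dosed fraction of 3 to 8% to 167 and obtain 0.03 × 167 = 5 to 0.08 × 167 = 13 patients. The documents support neither part: no fraction is given, and 167 includes 1704 participants whom the eligibility rules keep from rolling over. A claim that disposition is materially distorted therefore goes too far.

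The verdict assumes that SAF means dosed in 1705. The definition does not say so, but the SAP's periods and baseline (2.2.1, 2.2.2) are anchored to the first 1705 administration. Calling SAF the re-dosed patients would be inaccurate, since former placebo patients receive their first efgartigimod in 1705.

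**What to change.** - Put Tables 14.1.1.9 and 14.1.1.10 on RO, with a category for patients not dosed in 1705, since such patients belong to no cycle.
- Put Listings 16.2.1.1, 16.2.7.1 and 16.2.7.2 on RO, in line with 16.2.7.3 and with SAP 3.1 and 5.1.3.
- Keep SAF for TEAE, efficacy, PD and change-from-baseline tables.
- Amend the sentence in SAP 2.1.1 so that it names the outputs on RO, and add to the SAF definition that the dose is one given in 1705.
- In SAP 2.2.1, end ITP0 at the date of last contact for patients who are never dosed.
- In SAP 6.1, record that SAF replaces the population of Protocol 8.2 and 8.4.1 for the remaining analyses, with the reason.

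The cost is a population flag on two tables and three listings, one extra table category, one period-end rule and some SAP wording. Moving demographics to RO, or adding an AE overview of ITP0 time, would be optional. The overview would need further derivation rules.

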2.2 PHASES, PERIODS AND TIME POINTS

2.2.1 *Phases and periods*

All events and assessments will be allocated to phases and periods (see Table 1). A patient can start in 1705 in an inter-treatment period or in a cycle, depending on the patient status regarding the need for (re-)treatment upon roll-over. Each period following ITPO coincides with a cycle and includes the 4 administrations of efgartigimod and the inter-treatment period (ITP) visits. The length of the ITP is patient specific and can differ between the different periods. The number of patients may decline for each subsequent cycle.

	Statistical Analysis Plan	
ARGX-113-1705	Final Analysis	Final 1.0 of 20SEP2022

Table 1: phase/period definition

Phase	Period	Start	End
Treatment	ITP0	Earliest of (date of signing the informed consent form (ICF) and date of roll-over), with 00:00 added as time part.	First administration date/time in cycle 1 – 1 minute
	Cycle 1	First administration date/time in cycle 1	First administration date/time in next cycle – 1 minute or if last cycle: date of last contact, with 23:59 added as time part
	Cycle n	First administration date/time in cycle n	First administration date/time in next cycle – 1 minute or if last cycle: date of last contact, with 23:59 added as time part
	Cycle x	First administration date/time in cycle x	Date of last contact, with 23:59 added as time part

AEs and concomitant medications will be allocated to phases and periods as described in sections 5.1.2 and 3.5.2 respectively. All other assessments will be allocated to phases and periods based on the assessment date/time.

In case of (partially) missing date/time fields disabling allocation or date(time) equal to dosing date(time), information from visit label and protocol schedule of assessments (SoA) will be used to allocate to the correct period. If this is not possible, assessments will be allocated to the first possible cycle (not ITP0) unless the available parts of the assessments start or stop date/time provide evidence the assessments did not occur during that period.

